5.4.2.1 Events That Occur prior to Study Drug Initiation

After informed consent has been obtained but prior to initiation of study drug, only serious adverse events caused by a protocol-mandated intervention should be reported.

These events should be reported to the Sponsor or its designee immediately (i.e., no more than 24 hours after learning of the event) on the Adverse Event eCRF and submit the report via the electronic data capture (EDC) system. A report will be generated and sent to Safety Risk Management by the EDC system.

In the event that the EDC system is unavailable, the paper Clinical Trial Serious Adverse Event/Adverse Event of Special Interest Reporting Form provided to investigators should be completed and submitted to the Sponsor or its designee immediately (i.e., no more than 24 hours after learning of the event), either by faxing or by scanning and emailing the form using the fax number or email address provided to investigators.

5.4.2.2 Events That Occur after Study Drug Initiation

After initiation of study drug, serious adverse events and adverse events of special interest should be reported until 28 days after the final dose of study drug. Investigators should record all case details that can be gathered immediately (i.e., within 24 hours after learning of the event) on the Adverse Event eCRF and submit the report via the electronic data capture (EDC) system. A report will be generated and sent to Safety Risk Management by the EDC system.

In the event that the EDC system is unavailable, the paper Clinical Trial Serious Adverse Event/Adverse Event of Special Interest Reporting Form provided to investigators should be completed and submitted to the Sponsor or its designee immediately (i.e., no more than 24 hours after learning of the event), either by faxing or by scanning and emailing the form using the fax number or email address provided to investigators. Once the EDC system is available, all information will need to be entered and submitted via the EDC system.

Instructions for reporting serious adverse events that occur > 28 days after the final dose of study drug are provided in Section 5.6.

5.4.3 Reporting Requirements for Pregnancies

5.4.3.1 Pregnancies in Female Patients

Female patients of childbearing potential will be instructed to immediately inform the investigator if they become pregnant during the study or within 28 days after the final dose of study drug. A paper Clinical Trial Pregnancy Reporting Form should be completed and submitted to the Sponsor or its designee immediately (i.e., no more than 24 hours after learning of the pregnancy), either by faxing or by scanning and emailing the form using the fax number or email address provided to investigators. Pregnancy should not be recorded on the Adverse Event eCRF. The investigator should discontinue study drug and counsel the patient, discussing the risks of the pregnancy and the possible effects on the fetus. Monitoring of the patient should continue until conclusion of the pregnancy. Any serious adverse events associated with the pregnancy (e.g., an event in the fetus, an event in the mother during or after the pregnancy, or a congenital anomaly/birth defect in the child) should be reported on the

FHTR2163—Genentech, Inc. 61/Protocol GR42558, Version 4 Adverse Event eCRF. In addition, the investigator will submit a Clinical Trial Pregnancy Reporting Form when updated information on the course and outcome of the pregnancy becomes available.

5.4.3.2 Abortions

A spontaneous abortion should be classified as a serious adverse event (as the Sponsor considers abortions to be medically significant), recorded on the Adverse Event eCRF, and reported to the Sponsor immediately (i.e., no more than 24 hours after learning of the event; see Section 5.4.2).

If a therapeutic or elective abortion was performed because of an underlying maternal or embryofetal toxicity, the toxicity should be classified as a serious adverse event, recorded on the Adverse Event eCRF, and reported to the Sponsor immediately (i.e., no more than 24 hours after learning of the event; see Section 5.4.2). A therapeutic or elective abortion performed for reasons other than an underlying maternal or embryofetal toxicity is not considered an adverse event.

All abortions should be reported as pregnancy outcomes on the paper Clinical Trial Pregnancy Reporting Form.

5.4.3.3 Congenital Anomalies/Birth Defects

Any congenital anomaly/birth defect in a child born to a female patient exposed to study drug should be classified as a serious adverse event, recorded on the Adverse Event eCRF, and reported to the Sponsor immediately (i.e., no more than 24 hours after learning of the event; see Section 5.4.2).

5.5 FOLLOW-UP OF PATIENTS AFTER ADVERSE EVENTS

5.5.1 Investigator Follow-Up

The investigator should follow each adverse event until the event has resolved to baseline grade or better, the event is assessed as stable by the investigator, the patient is lost to follow-up, or the patient withdraws consent. Every effort should be made to follow all serious adverse events considered to be related to study drug or trial-related procedures until a final outcome can be reported.

During the study period, resolution of adverse events (with dates) should be documented on the Adverse Event eCRF and in the patient's medical record to facilitate source data verification.

All pregnancies reported during the study should be followed until pregnancy outcome.

5.5.2 Sponsor Follow-Up

For serious adverse events, adverse events of special interest, and pregnancies, the Sponsor or a designee may follow up by telephone, fax, email, and/or a monitoring visit to obtain additional case details and outcome information (e.g., from hospital discharge summaries, consultant reports, autopsy reports) in order to perform an independent medical assessment of the reported case.

5.6 ADVERSE EVENTS THAT OCCUR AFTER THE ADVERSE EVENT REPORTING PERIOD

The Sponsor should be notified if the investigator becomes aware of any serious adverse event that occurs after the end of the adverse event reporting period (defined as 28 days after the final dose of study drug), if the event is believed to be related to prior study drug treatment or to a protocol-mandated intervention (see Section 5.3.1). These events should be reported through use of the Adverse Event eCRF. However, if the EDC system is not available, the investigator should report these events directly to the Sponsor or its designee, either by faxing or by scanning and emailing the paper Clinical Trial Serious Adverse Event/Adverse Event of Special Interest Reporting Form using the fax number or email address provided to investigators.

5.7 EXPEDITED REPORTING TO HEALTH AUTHORITIES, INVESTIGATORS, INSTITUTIONAL REVIEW BOARDS, AND ETHICS COMMITTEES

The Sponsor will promptly evaluate all serious adverse events and adverse events of special interest against cumulative product experience to identify and expeditiously communicate possible new safety findings to investigators, IRBs, ECs, and applicable health authorities based on applicable legislation.

To determine reporting requirements for single adverse event cases, the Sponsor will assess the expectedness of these events through use of the reference safety information in the document listed below:

Drug	Document
FHTR2163	FHTR2163 Investigator's Brochure

The Sponsor will compare the severity of each event and the cumulative event frequency reported for the study with the severity and frequency reported in the applicable reference document.

Reporting requirements will also be based on the investigator's assessment of causality and seriousness, with allowance for upgrading by the Sponsor as needed.

6. STATISTICAL CONSIDERATIONS AND ANALYSIS PLAN

Data collected from the Week 72 or Week 76 visit of the parent study or the Day 1 visit of the OLE study will serve as baseline data for the OLE study.

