2.4 BIOMARKER OBJECTIVES

The exploratory imaging biomarker objective for this study is to evaluate GA disease status, in the study population and in subgroups based on *HTRA1* risk-variant carrier status as determined in the parent study, on the basis of the following endpoint:

• Change in GA area from parent study baseline and from OLE study baseline, as measured by fundus autofluorescence (FAF) imaging and determined by a central reading center consisting of graders and ophthalmologists experienced in the conduct of clinical trials

The exploratory biomarker objective for this study is to identify and/or evaluate biomarkers that are predictive of response to FHTR2163, are associated with rate of progression to a more severe disease state, are associated with susceptibility to developing adverse events, can provide evidence of FHTR2163 activity, or can increase the knowledge and understanding of disease biology and drug safety, on the basis of the following endpoints:

- Relationship between biomarkers in plasma and aqueous humor (listed in Section 4.5.7) and safety, PK, immunogenicity, or other biomarker endpoints
- Relationship between retinal imaging metrics (e.g., metrics from FAF, SD-OCT, optical coherence tomography angiography [OCT-A]) and safety, PK, immunogenicity, or other biomarker endpoints

3. STUDY DESIGN

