3.1 DESCRIPTION OF THE STUDY

Study GR42558 is a multicenter, OLE study to evaluate the long-term safety and tolerability of ITV injections of FHTR2163 in patients with GA who completed the parent study. Patients who discontinued from the parent study or discontinued from study treatment prior to completion of the final (Week 76) visit are not eligible for enrollment in this OLE study. Approximately 360 patients are expected to participate in the OLE study.

Patients who consent to participate in the OLE study will be screened for eligibility upon completion of the parent study (i.e., Week 76 visit). The Week 76 visit will serve as the final visit for the parent study and the first (Day 1) visit for the OLE study (i.e., the two visits are to be conducted on the same day), and all Week 76 assessments must be completed prior to conducting Day 1 assessments. If all assessments for the Day 1 visit cannot be completed on the same day as the Week 76 visit, patients may return to the clinic within 28 days to complete the Day 1 visit. If a patient is not able to complete the Day 1 visit within 28 days, the investigator must contact the Medical Monitor for further discussion prior to scheduling the Day 1 visit.

Patients will receive 20 mg of FHTR2163 or 10 mg of FHTR2163 by ITV injection in the same eye selected for injections in the parent study (referred to as the "study eye") Q4W or Q8W for approximately 144 weeks. Dosing frequency will remain consistent with each patient's original dosing schedule in the parent study (i.e., Q4W or Q8W). Upon implementation of protocol Version 4, all eligible patients in the sham control arms of the parent study that are newly enrolling in the OLE study will receive 10 mg of FHTR2163 (Q4W or Q8W; see Figure 1). Patients currently enrolled in the OLE study (i.e. enrolled prior to implementation of protocol Version 4) will continue receiving their current dosing regimen for the remainder of the study.

Figure 1 presents an overview of the study design. Schedules of activities are provided in Appendix 1 and Appendix 2.

FHTR2163—Genentech, Inc. 23/Protocol GR42558, Version 4

Figure 1 Study Schema

Q4W = every 4 weeks; Q8W = every 8 weeks.

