6.7 BIOMARKER ANALYSES

Mean change in GA area from parent study baseline and OLE study baseline, as measured by FAF imaging and determined by a central reading center, will be summarized by descriptive statistics. The relationship between change in GA area and *HTRA1* risk-variant status (i.e., carriers versus non-carriers of the *HTRA1* AMD risk variant, rs10490924) will be explored. Biomarkers will be analyzed together with PK data to explore PK/PD relationships. Additional analyses will be performed to identify biomarkers that are predictive of response to FHTR2163, are associated with rate of progression to a more severe disease state, are associated with susceptibility to developing adverse events, can provide evidence of FHTR2163 activity, or can increase the knowledge and understanding of disease biology and drug safety.

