Appendix 1: Schedule of Activities for Q4W Arms

	Day	/ 1 ª	Week (±5 days)																									
												Trea	atme	ent F	Perio	od V	/isits	6										
	PS ⁵	OLE	4	8	12	16	20	24	28	32	36	40	44	48	52	56	60	64	68	72	76	80	84	88	92	96	UV	ET℃
LL BCVA testing (starting at 4 m) ^k	Ex							х						x						x						х	Xf	x
IOP measurement ^k	Ex		х	х	х	х	х	х	х	х	х	х	х	х	х	х	х	х	х	х	х	х	х	х	х	х	х	х
Slit-lamp examination ¹	Ex		х	х	х	х	х	х	х	х	х	х	х	х	х	х	х	х	х	х	х	х	х	х	х	х	х	х
Aqueous humor sample ^{m, n}	Ex n							x						х						x						х	Xf	
Dilated binocular indirect ophthalmoscopy	Ex		x	x	x	x	х	x	x	x	x	x	x	x	x	x	x	x	x	x	x	x	x	x	x	x	Xf	x
FAF °	Ex							х						х						х						х	Xf	х
SD-OCT °		х		х		х		х		х		х		х		х		х		х		х		х		х	X ^{f, j}	х
OCT-A ^{o, p}	Ex							х						х						х						х	Xf	х
NI images °	Ex							х						х						х						х	Xf	х
Color fundus photography °	Ex													х												х	X ^{f, j}	х
Administration of study drug to study eye ^q		х	x	x	x	x	x	x	x	х	х	x	x	x	х	x	x	x	x	x	x	x	x	x	x	x		
Post-treatment finger counting and IOP measurement ^r		х	x	x	x	x	x	x	x	x	x	x	x	x	x	x	x	x	x	x	x	x	x	x	x	x		
Concomitant medications ^s	Ex		х	х	х	х	х	х	х	х	х	х	х	х	х	х	х	х	х	х	х	х	х	х	х	х	х	х
Adverse events t	Ex		х	х	х	х	х	х	х	х	х	х	х	х	х	х	х	х	х	х	х	х	х	х	х	х	х	х
Concurrent ocular procedures ^u	Ex		х	x	x	х	х	x	х	х	х	x	x	х	х	х	x	x	x	x	x	x	x	х	x	х	x	x
Follow-up call ^v		х	х	х	х	х	х	х	х	х	х	х	х	х	х	х	х	х	х	х	х	х	х	х	х	х		

Day 1–Week 96

Day 1–Week 96

ADA=anti-drug antibody; BCVA=best corrected visual acuity; CFP=color fundus photograph; ET=early termination; Ex=extracted data (from PS); FA=fluorescein angiography; FAF=fundus autofluorescence; FU=follow-up; IOP=intraocular pressure; IWRS=interactive web-based response system; LL BCVA=low-luminance BCVA; NI=near infrared; OCT-A=optical coherence tomography angiography; OLE=open-label extension; PK=pharmacokinetic; PS=parent study; Q4W=every 4 weeks; SD-OCT=spectral domain optical coherence tomography; UV=unscheduled visit.

Notes: All ocular assessments are to be performed for both eyes unless noted otherwise.

On treatment days, all assessments and sample collection should be completed prior to study drug administration, except for post-treatment finger counting and IOP measurement.

Patients who discontinue study drug prematurely should be strongly encouraged to stay in the study and undergo as many scheduled visits as possible.

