Appendix 1: Schedule of Activities for Q4W Arms

Day 1–Week 96

- ^j In case of Grade > 0 non-infectious intraocular inflammation, contact the Medical Monitor to discuss case. An additional serum ADA and PK sample should be collected as close as possible to the time of diagnosis. Consider performing CFP/FA (Appendix 12; widefield CFP/FA or standard CFP/FA with peripheral sweeps is preferred), SD-OCT, and uveitis lab workup as clinically indicated. Additionally, consider treatment with corticosteroids if appropriate, based on the individual patient presentation and comorbidities (e.g., diabetes, systemic hypertension), *and consider referring patient to a uveitis specialist and/or rheumatologist, per clinical judgment*.
- ^k Perform assessment prior to dilating the eyes.
- ¹ Perform slit-lamp examination prior to dilating eyes; for grading scales for anterior chamber flare or cells and vitreous cells, see Appendix 5.
- Aqueous humor sample must be collected from the study eye after pretreatment IOP measurement, but prior to study drug administration. For a detailed description of the anterior chamber paracentesis and aqueous humor sample collection procedures, see Appendix 13 and the laboratory manual.
- ⁿ If the Day 1 visit for the OLE is not performed on the same day as the Week 76 visit for the parent study, and serum PK and aqueous humor samples were not collected on Week 76, these samples should be collected on Day 1 of OLE study.
- Both eyes will be dilated prior to ocular imaging. FAF, SD-OCT, OCT-A (as applicable), NI images, and color fundus photographs will be obtained from both eyes and will be forwarded to the central reading center. If a patient misses a study visit where ocular images were scheduled to be obtained, the images should be obtained at the next scheduled visit.
- ^p OCT-A is mandatory for sites that have the capability.
- ^q All assessments (including a detailed examination to evaluate for signs of intraocular inflammation) and sample collection should be completed prior to study drug administration, except for post-treatment finger counting and IOP measurement.

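### The GA-area baseline image can precede the first OLE injection by 0 to 8 weeks, and the planned mean change makes no allowance for elapsed time

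*Combined protocol and SAP*

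**What the plan says.** The opening of Section 6 defines OLE baseline for all analyses: "Data collected from the Week 72 or Week 76 visit of the parent study or the Day 1 visit of the OLE study". It gives no order of preference.

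Section 3.1 plans the two visits as one: "The Week 76 visit will serve as the final visit for the parent study and the first (Day 1) visit for the OLE study". It then allows them to separate: "patients may return to the clinic within 28 days to complete the Day 1 visit". Longer gaps are not ruled out: "If a patient is not able to complete the Day 1 visit within 28 days, the investigator must contact the Medical Monitor", and no upper limit is given.

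In the schedules of activities (Appendix 1 for Q4W, Appendix 2 for Q8W), the FAF row is marked as extracted from the parent study and has no entry under OLE Day 1. SD-OCT, by contrast, is scheduled at OLE Day 1. Follow-up FAF falls at Weeks 24, 48, 72, 96, 120 and 144. If a visit with scheduled imaging is missed, "the images should be obtained at the next scheduled visit".

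The endpoint in Section 2.4 is "Change in GA area from parent study baseline and from OLE study baseline". Section 6.7 plans to summarize "Mean change in GA area from parent study baseline and OLE study baseline" descriptively. It mentions no annualization, slope, visit window or adjustment for actual time, and no breakdown by arm. An annualized GA growth rate appears only in Section 6.3, as a baseline characteristic.

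**The concern.** The plan treats GA as a progressive lesion, so a difference between two images depends on the time between them. Change from OLE baseline is meant to describe what happened during the extension. If the baseline image predates the first OLE injection, the change also contains growth from before the extension, by an amount that can vary from patient to patient.

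For patients who came from the sham arms, that earlier growth is untreated, yet it would be counted as change in the OLE. The distortion is largest at the earliest imaging visit, where the true interval is shortest. Missed images add a second source of uneven timing, because the replacement comes at the next visit and the plan does not say how it is labelled.

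The plan handles a similar gap for other data. A footnote in both appendices has serum PK and aqueous humor samples taken on Day 1 when the visits are separated and the Week 76 samples were not collected. No matching provision covers FAF.

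**Working it through.** The plan states no figure for the baseline interval, so there is nothing to reproduce. The check is calendar arithmetic.

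**Inputs.** Possible FAF baseline visits: parent Week 72 or Week 76 (Section 6; Day 1 drops out because no FAF is scheduled then). Delay of Day 1 after Week 76: 0 to 28 days (Section 3.1). First OLE injection: Day 1 (Appendices 1 and 2). FAF visits: Weeks 24 to 144, every 24 weeks.

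**Step 1: gap between baseline image and first OLE injection.** Gap in weeks = (76 − baseline week) + (delay in days)/7.

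- Week 76 image, no delay: 0 + 0 = 0 weeks
- Week 76 image, 28-day delay: 0 + 28/7 = 4 weeks
- Week 72 image, no delay: 4 + 0 = 4 weeks
- Week 72 image, 28-day delay: 4 + 28/7 = 8 weeks

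Within the 28-day allowance the range is 0 to 8 weeks. A longer delay agreed with the Medical Monitor would extend it.

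**Step 2: excess as a share of the intended interval.** Assuming linear growth, excess = gap / weeks since Day 1.

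| Weeks since Day 1 | Gap 4 weeks | Gap 8 weeks |
|---|---|---|
| 24 | 4/24 = 16.7% | 8/24 = 33.3% |
| 48 | 8.3% | 16.7% |
| 72 | 5.6% | 11.1% |
| 96 | 4.2% | 8.3% |
| 120 | 3.3% | 6.7% |
| 144 | 2.8% | 5.6% |

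**Step 3: scale in area.** The documents give no growth rate. Assume 1.0 to 2.5 mm²/year, for scale only. Excess area = rate × gap × 7/365.25.

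- Gap of 4 weeks: 0.08 to 0.19 mm²
- Gap of 8 weeks: 0.15 to 0.38 mm²
- True 24-week growth, for comparison: 0.46 to 1.15 mm²

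**Step 4: does dividing by actual time cure it?** Let growth be g per week and take the 8-week gap at Week 24. Observed change is g × (24 + 8) = 32g. Read as a 24-week change, this implies 32g/24 = 1.33g per week. Divided by the actual interval, it gives 32g/32 = g. The timing error drops out whichever visit supplied the image.

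**The case against.** The strongest reply is that Section 6 may not offer a choice for each patient. Its sentence covers every variable, and the schedules give each assessment one source, so it may simply list the visits at which different variables were collected. The parent study's imaging schedule is not in these documents. If parent FAF was always taken at Week 76 and Day 1 fell on the same day, the gap is zero. If it was always taken at Week 72, that part of the gap is a constant 4 weeks, equal across arms. This stands, and it is why the range must start at 0. It does not remove the point: a constant 4 weeks still overstates absolute change, and the Day 1 delay still varies by patient.

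It is also fair that GA area is exploratory and descriptive, and that change from parent-study baseline does not depend on which visit supplies the OLE baseline (a Day 1 delay can still shift its timing).

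Three stronger readings are tempting, and the documents do not support them.

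- A reader might infer that raw change will be tabulated by nominal visit. Section 6.7 does not say so; it is silent on visit grouping.
- A reader might combine the earliest baseline, the full delay and a missed Week 24 image into one much larger overstatement. That describes a single extreme patient, whereas the reported quantity is a mean. It also needs the late image to keep the label of the missed visit, and no such rule is stated.
- A reader might expect a spurious dosing-frequency effect, since a replacement image comes 4 weeks later in Q4W and 8 weeks later in Q8W. The baseline rules are the same for both regimens, so only missed images could differ. If 5% to 10% of patients missed Week 24 (an assumption) and all late images kept that label, mean elapsed time would rise by 0.2 to 0.4 weeks in Q4W (0.05 × 4 to 0.10 × 4) and 0.4 to 0.8 weeks in Q8W (0.05 × 8 to 0.10 × 8). The difference of 0.2 to 0.4 weeks is 0.8% to 1.7% of 24 weeks. The extension is non-randomized, and Section 6.7 plans no comparison of GA area between regimens.

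**Conclusion.** The point holds as a limited one. Followed as written, the plan lets change in GA area from OLE baseline include 0 to 4 weeks of earlier growth with a Week 76 image, or 4 to 8 weeks with a Week 72 image, and it specifies nothing to account for that time. At the upper end this is one third of a 24-week change, falling to about 6% at Week 144.

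The percentages assume linear growth and a Day 1 delay within 28 days. How many patients are affected cannot be determined here, because neither the parent FAF schedule nor the frequency of delayed Day 1 visits is given. The primary safety analysis is unaffected. The change is worth making because a better summary is available at almost no cost, not because a main conclusion depends on it.

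**What to change.** In Section 6.7, report change in GA area from OLE baseline as an annualized rate (mm²/year) computed from the actual FAF image dates, by arm, alongside or in place of raw mean change. Section 6.3 already uses an annualized growth rate at baseline, so the measure is not new to the plan.

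In Section 6, state that OLE baseline is the last non-missing value on or before the first OLE injection. This removes discretion but does not close the gap by itself: where the last FAF is a Week 72 image, it stays the baseline. The actual-date rate is what corrects the timing.

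One limit should be acknowledged in the report. If treatment changes the growth rate, the annualized rate in a former sham patient still blends untreated and treated time: 4/28 = 14% of the interval at Week 24 with a 4-week gap, and 8/32 = 25% with an 8-week gap.

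The cost is two sentences and a little extra analysis. No new assessment is needed. Images go to a central reading center, so acquisition dates should be available, although the documents do not say so explicitly.
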